7.5.5.2 Tonometry

Goldmann measurements of IOP and its change from baseline will be summarized descriptively at each visit.

7.5.5.3 Slit Lamp and Fundus Examination Findings

Numbers and percentages of eyes will be summarized for each of the findings at visit.

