 - o No visible damage to either the PCIOL or the IOPCL
 - o Uniform leaflet coverage of all IOPCL haptic tabs
- Long-term adherence and positional stability
 - Minimal Change in uniformity of the gap between 1-2 months and 4-6-months as determined by UBM measurements. Minimal change is defined as +/- 10 microns between visits is established and maintained using UBM imaging
- Characterization and incidence of cumulative and persistent intraoperative and post-operative adverse events.

Stopping Rules

The Sponsor or the clinical investigator can suggest suspension of the clinical trial at any time if they are in receipt of information that leads them to believe that continuing the study jeopardizes the health and welfare of the clinical trial participants. Suspension of the study will be considered if two or more consecutive severe ocular injuries occur at any one clinical site that are related to the surgical procedure and/or IOPCL device. A severe ocular injury results in a permanent impairment of a vision or permanent damage to an eye.

Examples:

- Uveitis-Glaucoma-Hyphema (UGH) Syndrome. Intraocular chafing from the IOL/PCIOL implant leading to a spectrum of iris transillumination defects and pigmentary dispersion to microhyphemas with elevated intraocular pressure.
- Posterior capsule rupture with IOL/PCIOL dislocation resulting in a posterior vitrectomy during the surgical procedure

Primary Effectiveness Endpoint

Proportion of eyes ($\geq 50\%$) able to achieve a stable target refraction, (manifest or autorefraction) within 0.5 D of the intended target. Stability is achieved when there is no change (± 0.50 D) within two consecutive postoperative visits at 1 month or later visits.

04-08-2021 5

3. Subject Population

A maximum of 10 pseudophakic eyes will be implanted unilaterally with the AccuraSee IOPCL.

3.1. Inclusion Criteria:

- 1. Subjects who have already had cataract surgery with a Bausch and Lomb monofocal intraocular lens model LI61A0 (with lens power from 18.0 diopters (D) to 23.0 D) or model LI61SE (with a lens power from18.0 D to 22.5 D), as clearly evidenced by photographic documentation with one of the following: (1) patient medical record, (2) clinic chart with labeling attached, (3) surgical record with labeling attached, or (4) patient identification card with make, model, power, and serial number.
- 2. Able to comprehend and sign a statement of informed consent.

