10.2 Unscheduled / Interim Visits

Additional visits may be scheduled as deemed necessary by the investigator, to ensure the safety and well-being of the subject.

11. Clinical Assessments

All parameters will be recorded for both eyes at baseline (pre-operative). Measurements will be recorded for the study eye at postoperative and post-removal visits. See Appendix 2A schedule of visits (pre and post-operative visits) and Appendix 2B (post-removal visits). See Appendix 3 for clinical assessment instructions

- Inclusion/exclusion criteria: Preoperative
- Medical history: Preoperative
- Demographics: Preoperative
- Patient Informed Consent: Preoperative
- Measurements: Make and Model # of Equipment Preoperative
- Axial Length & Keratometry Preoperative
- Capsulorhexis Size at the time of IOL surgery: Preoperative
- Position of IOL Haptics and IOPCL Incision Location: Preoperative
- Mesopic and Photopic Pupil size measured by Pupilometer: Preoperative

- Predicted Post-Op Refraction: Preoperative
- Pseudophakic IOL power with make and model number: Preoperative
- Spatial Visualization between the PCIOL and IOPCL Using UBM: 30-60 days, 120-180 days, 330-420 days, Interim.
- Recording of the IOPCL Surgical Procedure: Operative
- UCDVA: Uncorrected Distance Visual Acuity Preoperative, 7-14 days, 30-60 days, 120-180 days, 330-420 days. Interim
 - Post-removal, 7-14 days, 30-60 days, 120-180 days, 330-420 days. Interim
- UCIVA: Uncorrected Intermediate Visual Acuity Preoperative, 7-14 days, 30-60 days, 120-180 days, 330-420 days. Interim
 - Post-removal, 7-14 days, 30-60 days, 120-180 days, 330-420 days. Interim
- UCNVA: Uncorrected Near Visual Acuity Preoperative, , 7-14 days, 30-60 days, 120-180 days, 330-420 days, Interim.
 - Post-removal, 7-14 days, 30-60 days, 120-180 days, 330-420 days. Interim
- BCDVA: Best Corrected Distance Visual Acuity Preoperative, 7-14 days, 30-60 days, 120-18 days, 330-420 days, Interim
 - Post-removal, 7-14 days, 30-60 days, 120-180 days, 330-420 days, Interim
- Manifest Refraction: Preoperative, 7-14 days, 30-60 days, 120-180 days, 330-420 days, Interim
 - Post-removal, 7-14 days, 30-60 days, 120-180 days, 330-420 days, Interim
- Auto-refraction: Preoperative, 7-14 days, 30-60 days, 120-180 days, 330-420 days. Interim
 - Post-removal, 7-14 days, 30-60 days, 120-180 days, 330-420 days, Interim.
- Slit Lamp Examination: Preoperative, 1-2 days, 7-14 days, 30-60 days, 120-180 days, 330-420 days. Interim

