- ➤ Malpositioned/Misaligned Optics (IOPCL not centered over PCIOL)
 - o Early[1]
 - o Late[2]
- Unseated IOPCL haptic tabs (One or more haptic tabs not securely attached to the PCIOL)

- > Post Nd:YAG Posterior capsulotomy event
- > Lens Optical Performance
- Mechanical Failure
- Vitreous Aspiration for Pupillary Block
- Corneal Stroma Edema
 - Corneal Edema with BCDVA of 20/40 or worse at Form 3 (1-2M post-op) or later
- > Iritis present at 1-month or later
- Macular Edema present at 1-month or later
- > Raised IOP requiring treatment
 - Raised IOP, greater than 10 mmHg above baseline and to a minimum of 25 mmHg.
- ➤ Iris Chafing
- > Iris Trauma and/or Damage
- > Iris Transillumination Defects
- > Pigment Dispersion
- > Pseudophacodonesis or Evidence of Zonular Trauma/dehiscence
- > Inter-device opacification or fibrosis between the PCIOL and IOPCL
- > Other

```
[1]Early – prior to Form 4 visit window (i.e., < 120 days)
[2]Late – At 120 days or later
```

Note: Secondary Surgical Intervention(s) (SSI) may be necessary to resolve any of the adverse events identified above. If an SSI is conducted in the trial, the details of the SSI and corresponding reason for SSI will be documented on the SSI CRF.

Examples of Secondary Surgical Interventions

- ➤ Irrigation of IOPCL/IOL Interface
- > Exchange
- ➤ Reposition of the same Implantable Pseudophakic Contact Lens
- ➤ Removal

13. Adverse Experience and Complication Reporting

Throughout the course of the proposed study, all efforts will be made to remain alert to possible adverse experiences or untoward findings. If adverse experiences occur, the first concern will be the safety and welfare of the subject and appropriate medical intervention will be made. Any adverse experiences observed by the investigator or reported by the subjects, whether or not ascribed to the investigational procedure or device, will be recorded on the subjects' adverse event case report form. A new adverse event case report form is used for each adverse event or adverse event related visit.

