7.5.1 Preservation of BCDVA

The analysis of this clinical outcome will be based on the observed data of AccuraSee IOPCL. The number and percent of IOPCL implanted eyes with a BCDVA loss of 2 or more lines from preoperative will be derived.

Additionally, if needed, data listing or summary will be provided for eyes with a BCDVA loss of ≥ 2 lines from the best BCDVA before the corresponding visits.

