7.5.4 Adverse Events

For each adverse event, number and percent of eyes reported with the event will be summarized at each scheduled visit (including intraoperatively) and during the study (i.e. cumulative and persistent).

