7.5.5.4 Visual Symptoms

For each symptom of the Quality of Vision (QoV) at each specified visit, the number and percent of subjects of the findings will be summarized. Additionally, the subscale score and overall score based on the QoV user manual will be calculated for each subject. These subscale score and overall score will be summarized based on mean, standard deviation, minimum, and maximum. Similar descriptive statistics will be prepared for the change in the QoV from preoperative.

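### SAP 7.5.5.3 counts slit-lamp findings by visit only; for findings that can exist before implantation, this leaves the number of newly affected eyes undetermined if findings resolve or visits are missed

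*SAP*

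**What the plan says.** SAP 7.5.5.3 consists of one sentence: "Numbers and percentages of eyes will be summarized for each of the findings at visit". It plans no shift table, no listing and no comparison with the preoperative examination.

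The baseline is collected. Protocol section 11 schedules "Slit Lamp Examination: Preoperative, 1-2 days, 7-14 days, 30-60 days, 120-180 days, 330-420 days. Interim", that is, one examination before surgery and five scheduled ones after it.

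Other safety sections of the SAP do compare each eye or subject with its own baseline:

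- BCDVA, SAP 7.5.1: "The number and percent of IOPCL implanted eyes with a BCDVA loss of 2 or more lines from preoperative will be derived".
- Tonometry, SAP 7.5.5.2: "IOP and its change from baseline will be summarized descriptively at each visit".
- Quality of vision, SAP 7.5.5.4: "Similar descriptive statistics will be prepared for the change in the QoV from preoperative".

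Adverse events are handled separately. SAP 7.5.4 states "For each adverse event, number and percent of eyes reported with the event will be summarized at each scheduled visit", and adds cumulative and persistent counts over the study. The postoperative event list in Protocol section 12 includes items seen at the slit lamp, such as "Iris Transillumination Defects", iris chafing and pigment dispersion. It does not say whether such an item must be new or worse than before surgery. SAP 6.5 uses available data without imputation.

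**The concern.** Counts at separate visits show how many eyes have a finding on each occasion. They do not show whether these are the same eyes. Every eye here has already had cataract surgery, and the study is aimed at eyes with ocular pathology, so some findings (pigment, corneal or capsular changes, transillumination defects) may be present before the AccuraSee goes in. The percentage can then stay flat or fall while a different eye acquires the finding.

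The concern is confined to findings that can pre-exist. Unseated haptic tabs, IOPCL malposition and inter-device opacification cannot, so the question of old versus new does not arise for them.

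The question is clinically relevant. The first example of a severe ocular injury under the stopping rules in Protocol section 2 describes "Intraocular chafing from the IOL/PCIOL implant leading to a spectrum of iris transillumination defects and pigmentary dispersion to microhyphemas". What is at stake is whether a reader of the report can tell how many eyes developed something new after implantation.

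**Working it through.** The plan gives no figure on this point, so there is nothing to reproduce. The finding counts below are assumed, to show what the planned table can and cannot determine.

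**Inputs.** n = 10 eyes, the maximum in SAP 6.2. One preoperative and five scheduled postoperative slit-lamp examinations (Protocol section 11). Available data only (SAP 6.5). I take the preoperative count to be tabulated as well, since SAP 7.2 summarizes preoperative parameters.

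**1. All eyes seen, findings can resolve.** Let a eyes have the finding before, b after, and k on both occasions. New cases = b − k. Since k lies between max(0, a + b − n) and min(a, b), new cases lie between max(0, b − a) and min(b, n − a).

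| Before | After | Fewest new | Most new |
|---|---|---|---|
| 1/10 | 1/10 | max(0, 0) = 0 | min(1, 9) = 1 |
| 2/10 | 2/10 | max(0, 0) = 0 | min(2, 8) = 2 |
| 3/10 | 3/10 | max(0, 0) = 0 | min(3, 7) = 3 |
| 3/10 | 1/10 | max(0, −2) = 0 | min(1, 7) = 1 |
| 0/10 | 2/10 | max(0, 2) = 2 | min(2, 10) = 2 |

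So 3/10 then 3/10 fits 0% to 30% of eyes newly affected. The upper end needs all three original cases to resolve. With no preoperative case (last row), the number new at that visit is exact.

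**2. All eyes seen, nothing resolves.** Then k = a and new cases = b − a. Equal counts mean exactly 0 new, and the planned table loses nothing.

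**3. Nothing resolves, one eye missed.** Take 3/10 then 3/9. If the missed eye had the finding, 2 cases carry over and 3 − 2 = 1 is new (1/9 = 11%). If it did not, 3 carry over and 0 are new. The result is 0 or 1. Accountability by visit (SAP 7.1) shows that an eye was missed, not whether it had the finding.

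**4. Across the five postoperative visits.** Take 0/10 before surgery and 1/10 at every visit. If it is the same eye each time, 1 eye was affected; if each case resolves and another eye follows, 5 were (10% to 50%). For an item reported as an adverse event, the cumulative count in SAP 7.5.4 gives the number of different eyes and removes this range. The range therefore applies only to slit-lamp findings not reported as adverse events.

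**5. Will any eye have a given finding before surgery?** The documents give no prevalence. If a proportion p of eyes has it, independently, the chance that at least one of 10 does is 1 − (1 − p)^10. For assumed p of 0%, 5%, 10% and 30% this is 0%, 40%, 65% and 97%. The exclusions in Protocol 3.2 favor the lower part of that range.

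**The case against.** The strongest reply is that the adverse-event tables already do this work. Protocol section 12 lists the main iris findings and ends with an open category. Section 13 requires adverse experiences to be recorded whether or not they are attributed to the device, and SAP 7.5.4 counts eyes cumulatively. Collection starts at surgery, so a stable old finding is not naturally a postoperative event. If one were reported, the count would be too high; it would not hide a newly affected eye.

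Much of this stands. For a listed event that no eye had before surgery, the number of different eyes is available, given proper reporting. It does not stand for pre-existing findings, because without a baseline rule the cumulative count can mix old and new cases. Nor does it cover a slit-lamp finding that is never reported as an event.

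A reader might infer from the stopping-rule example that this gap weakens the monitoring of severe injury. The documents do not support that. The protocol defines a severe ocular injury by permanent impairment or damage, which does not resolve, so only the missed-visit ambiguity in step 3 would remain. No stopping rule uses this table.

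It is also fair that slit lamp is listed under other clinical outcomes (SAP 3.3), not among the safety endpoints (SAP 3.2). IOP and quality of vision are numeric measures and therefore loose precedents; BCDVA loss is the close one.

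**Conclusion.** The point holds in a limited form. For slit-lamp findings that can exist before implantation, the planned counts do not give the number of newly affected eyes when a finding can resolve (3/10 then 3/10 fits 0 to 3) or when an eye is missed (3/10 then 3/9 fits 0 or 1 without resolution). The gap left after the adverse-event tables is pre-existing findings and findings not reported as events.

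Two further inferences are not supported. The range of 1 to 5 eyes should not be applied to transillumination defects, iris chafing or pigment dispersion reported as adverse events with no preoperative case. Nor does the gap show that the study's safety conclusion would be wrong: no endpoint depends on this table.

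The conclusion assumes that some findings are present before surgery and either resolve or fall in an eye with a missed visit. How often that happens cannot be determined from the documents. This is a minor point, worth fixing because the fix costs so little.

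**What to change.** Keep the by-visit counts and add to SAP 7.5.5.3:

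> For each slit-lamp finding recorded both before and after surgery, a by-eye shift table or listing will give, at each postoperative visit, the number and percent of eyes with a finding that was absent at that eye's preoperative examination, out of eyes examined on both occasions. The cumulative number of eyes with any new finding, including those seen at interim visits, will also be given. Worsening will be reported only for findings graded preoperatively on the same scale.

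Report SUN grades as observed, since Protocol section 11 schedules no preoperative grade. Limit the addition to the slit lamp: the same section lists no fundus examination.

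The cost is the SAP wording and one table or listing for at most 10 eyes. No visit or procedure is added. This assumes that the preoperative and postoperative case report forms, which are not in the available text, record the same slit-lamp items. The sponsor should confirm that first.

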7.5.5.4 Visual Symptoms

For each symptom of the Quality of Vision (QoV) at each specified visit, the number and percent of subjects of the findings will be summarized. Additionally, the subscale score and overall score based on the QoV user manual will be calculated for each subject. These subscale score and overall score will be summarized based on mean, standard deviation, minimum, and maximum. Similar descriptive statistics will be prepared for the change in the QoV from preoperative.

8 CHANGES FROM PLANNED ANALYSES

8.1 Changes from the Original Protocol

Version 2.0 – None

Version 3.0 – Add subgroup analyses for effectiveness due to the first 3 eyes having poor preoperative BCDVA with underlying pathology.

Version 4.0 – Updated study objective to match clinical study protocol. Add effectiveness analysis using autorefraction measurements. Revised subgroup analyses for effectiveness to subjects having poor preoperative BCDVA with underlaying pathology (removed first 3 eyes language).

Version 5.0 – Added analysis to evaluate the impact of surgical technique on IOPCL stability.

